6.1 Stopping Criteria

The DMC will give their overall opinion as to the safety to proceed with the study, if there are any suggested protocol modifications, or if the intervention should be stopped.

7.0 DMC Reporting: The DMC will not share confidential information, particularly trial interim data with anyone external to the DMC. The recommendations/decisions of the DMC will be communicated in writing to the PI, IRB, and/or appropriate regulatory agency. The JCRC IRB is the IRB of record.

8.0 Adverse Event Reporting - Summary

Any research-related SAE is required to be reported to the IRB. The summary of Adverse Event reporting and timeline is as follows.

Grade	Serious	Unexpected	Possibly Related	Where is this reported?	Timeline of Reporting
1-2	No	±	±	None	N/A
3-4	No	±	±	Clinical AE CRF	DMC & Annual IRB Reporting
Any	Yes	No	±	Clinical AE CRF	DMC & Annual IRB Reporting
Any	Yes	Yes	No	Clinical AE CRF	≤ 3 working days to IRB, Aggregate reporting to Sponsor
Any	Yes	Yes	Yes	Clinical AE CRF	≤ 3 working days to IRB and to Sponsor [†]
Lab Value	No	No	None	Blood Results CRF	DMC & Annual IRB Reporting

8.4. Interim Analysis

N/A

9. QUALITY CONTROL AND QUALITY ASSURANCE

During study conduct periodic monitoring may be conducted to ensure that the protocol and Good Clinical Practices (GCPs) are being followed. The monitors may review source documents to confirm that the data

recorded on CRFs is accurate. Additionally, the study site may be subject to review by the Institutional Review Board (IRB) and/or to inspection by appropriate regulatory authorities.

10. DATA HANDLING/RECORD RETENTION

10.1. Case Report Forms (CRF)/Electronic Data Record

A CRF is required and should be completed for each included subject.

The investigator has ultimate responsibility for the collection and reporting of all clinical, safety and laboratory data entered on the CRFs and any other data collection forms (source documents) and ensuring that they are accurate, authentic / original, attributable, complete, consistent, legible, timely (contemporaneous), enduring and available when required. The CRFs must be signed by the investigator or by an authorized staff member to attest that the data contained on the CRFs is true. Any corrections to entries made in the CRFs, source documents must be dated, initialed and explained (if necessary) and should not obscure the original entry.

10.2. Record Retention

To enable evaluations and/or audits, the investigator agrees to keep records, including the identity of all participating patients (sufficient information to link records, eg, CRFs and hospital records), all original signed informed consent documents, copies of all CRFs, safety reporting forms, source documents, and detailed records of treatment disposition, and adequate documentation of relevant correspondence (eg, letters, meeting minutes, telephone calls reports).

Investigator records must be kept for as long as required by applicable local regulations (UNCST generally requires a minimum of 5 years). When more than one requirement can be applied, records must be maintained for the longest period provided.

10.3. Confidentiality

Clinical data will be entered into a study specific database by designated staff on a regular basis from completed Case Record Forms (CRF) using REDCap. Consents and other source documents will be kept in locked cabinets. Data will be entered on a regular basis to ensure that it is up to date. The database will be entered on regular basis on a secure PCAccess to database will be given to authorized personnel only (members of the immediate study team) and a log of authorized personnel will be stored in the trial master file. Trial documents will be kept in locked cabinets. No participant identifying information will be disclosed in any publication or at any conference activities arising from the study.

11. ETHICS

11.1. Institutional Review Board (IRB)

It is the responsibility of the investigator to have prospective approval of the study protocol, protocol amendments, informed consent documents, and other relevant documents from the IRB. All correspondence with the IRB should be retained in the regulatory or trial master file. Copies of IRB approvals should be filed with other study documents.

11.2. Ethical Conduct of the Study

The study will be conducted in accordance with legal and regulatory requirements, as well as the general principles set forth in the International Ethical Guidelines for Biomedical Research Involving Human Subjects and the Declaration of Helsinki.

In addition, the study will be conducted in accordance with the protocol, GCP guidelines, DSMP, and applicable local regulatory requirements and laws.

11.3. Subject Information and Consent

All parties will ensure protection of subject personal data and will not include subject names on any forms, reports, publications, or in any other disclosures, except where required by laws. The informed consent document used in this study, and any changes made during the course of the study, must be prospectively approved by the IRB.

The investigator, or a person designated by the investigator, will obtain written informed consent from each subject before any study-specific activity is performed. The investigator will retain the original of each subject's signed consent document.

Given these individuals have depression at the start of the study we will re-affirm consent at the second study visit.

12. DEFINITION OF END OF TRIAL

When the last subject has had their chart checked for viral load testing data.

13. PUBLICATION OF STUDY RESULTS

We plan to present the findings of this study at an international conference such as CROI or IAS as well as some smaller mental health conferences. We will also prepare and submit the findings for publication in a peer reviewed scientific journal. We will present at Makerere, IDI or University of Minnesota forums as opportunities arise. Finally, we will hold forums at the clinics from which we enrolled to inform the staff and participants of our findings.

14. CAPACITY BUILDING

A group psychotherapy method, which has been validated in Uganda, will be used at IDI and/or KCCA clinics. Individuals in Kampala will be trained in how to do this and IDI could evaluate if this was something worth continuing.

15. FUNDING

The PI, [name], as applied for a K23 from the USA National Institute of Mental Health, part of the National Institute of Health, under grant number K23MH121220-01. It is pending funding. She also has additional startup funds at the University of Minnesota.

17.1. PATIENT HEALTH QUESTIONNAIRE (PHQ-9)**DATE-----**

Over the last 2 weeks, how often have you been
bothered by any of the following problems?
(use "· to indicate your answer)

	Not at all	Several days	More than half the days	Nearly every day
1. Little interest or pleasure in doing things	0	1	2	3
2. Feeling down, depressed, or hopeless	0	1	2	3
3. Trouble falling or staying asleep, or sleeping too much	0	1	2	3
4. Feeling tired or having little energy	0	1	2	3
5. Poor appetite or overeating	0	1	2	3
6. Feeling bad about yourself- or that you are a failure or have let yourself or your family down	0	1	2	3
7. Trouble concentrating on things, such as reading the newspaper or watching television	0	1	2	3
8. Moving or speaking so slowly that other people could have noticed. Or the opposite - being so fidgety or restless that you have been moving around a lot more than usual	0	1	2	3
9. Thoughts that you would be better off dead, or of hurting yourself	0	1	2	3

add columns

+

+

(Healthcare professional: For interpretation of TOTAL, TOTAL:

10. If you checked off *any problems*, how *difficult* have these problems made it for you to do your work, take care of things at home, or get along with other people?

Not difficult at all

Somewhat difficult

Very difficult

Extremely difficult

Copyright© 1999 Pfizer Inc. All rights reserved. Reproduced with permission. PRIME-MD© is a trademark of Pfizer Inc.

A2663B 10-04-2005

PHQ-9 Patient Depression Questionnaire

For initial diagnosis:

1. Patient completes PHQ-9 Quick Depression Assessment.
2. If there are at least 4 ✓ s in the shaded section (including Questions #1 and #2), consider a depressive disorder. Add score to determine severity.

Consider Major Depressive Disorder

- if there are at least 5 ✓ s in the shaded section (one of which corresponds to Question #1 or #2)

Consider Other Depressive Disorder

- if there are 2-4 ✓ s in the shaded section (one of which corresponds to Question #1 or #2)

Note: Since the questionnaire relies on patient self-report, all responses should be verified by the clinician, and a definitive diagnosis is made on clinical grounds taking into account how well the patient understood the questionnaire, as well as other relevant information from the patient.

Diagnoses of Major Depressive Disorder or Other Depressive Disorder also require impairment of social, occupational, or other important areas of functioning (Question #10) and ruling out normal bereavement, a history of a Manic Episode (Bipolar Disorder), and a physical disorder, medication, or other drug as the biological cause of the depressive symptoms.

To monitor severity over time for newly diagnosed patients or patients in current treatment for depression:

1. Patients may complete questionnaires at baseline and at regular intervals (eg, every 2 weeks) at home and bring them in at their next appointment for scoring or they may complete the questionnaire during each scheduled appointment.
2. Add up ✓ s by column. For every ✓ : Several days = 1 More than half the days = 2 Nearly every day = 3
3. Add together column scores to get a TOTAL score.
4. Refer to the accompanying **PHQ-9 Scoring Box** to interpret the TOTAL score.
5. Results may be included in patient files to assist you in setting up a treatment goal, determining degree of response, as well as guiding treatment intervention.

Scoring: add up all checked boxes on PHQ-9

For every ✓ Not at all = 0; Several days = 1; More than half the days = 2; Nearly every day = 3

Interpretation of Total Score

Total Score	Depression Severity
1-4	Minimal depression
5-9	Mild depression
10-14	Moderate depression
15-19	Moderately severe depression
20-27	Severe depression

17.2. Hamilton Rating Scale for Depression (17-items)

Instructions: For each item select the “cue” which best characterizes the patient during the past week.

1. DEPRESSED MOOD

(sadness, hopeless, helpless, worthless)

- 0 Absent
- 1 These feeling states indicated only on questioning
- 2 These feeling states spontaneously reported verbally
- 3 Communicates feeling states nonverbally, i.e., through facial expression, posture, voice and tendency to weep
- 4 Patient reports VIRTUALLY ONLY these feeling states in his spontaneous verbal and nonverbal communication

2. FEELINGS OF GUILT

- 0 Absent
- 1 Self-reproach, feels he has let people down
- 2 Ideas of guilt or rumination over past errors or sinful deeds
- 3 Present illness is a punishment. Delusions of guilt
- 4 Hears accusatory or denunciatory voices and/or experiences threatening visual hallucinations

3. SUICIDE

- 0 Absent
- 1 Feels life is not worth living
- 2 Wishes he were dead or any thoughts of possible death to self
- 3 Suicide ideas or gesture
- 4 Attempts at suicide (any serious attempt rates 4)

4. INSOMNIA - EARLY

- 0 No difficulty falling asleep
- 1 Complains of occasional difficulty falling asleep i.e., more than $\frac{1}{2}$ hour
- 2 Complains of nightly difficulty falling asleep

5. INSOMNIA - MIDDLE

- 0 No difficulty
- 1 Patient complains of being restless and disturbed during the night
- 2 Waking during the night – any getting out of bed rates 2
(except for purposes of voiding)

6. INSOMNIA - LATE

- 0 No difficulty
- 1 Waking in early hours of the morning but goes back to sleep
- 2 Unable to fall asleep again if gets out of bed

7. WORK AND ACTIVITIES

- 0 No difficulty
- 1 Thoughts and feelings of incapacity, fatigue or weakness related to activities; work or hobbies
- 2 Loss of interest in activity; hobbies or work – either directly reported by patient, or indirect in listlessness, indecision and vacillation (feels he has to push self to work or activities)
- 3 Decrease in actual time spent in activities or decrease in productivity. In hospital, rate 3 if patient does not spend at least three hours a day in activities (hospital job or hobbies) exclusive of ward chores.
- 4 Stopped working because of present illness. In hospital, rate 4 if patient engages in no activities except ward chores, or if patient fails to perform ward chores unassisted.

8. RETARDATION

(slowness of thought and speech; impaired ability to concentrate; decreased motor activity)

- 0 Normal speech and thought
- 1 Slight retardation at interview
- 2 Obvious retardation at interview
- 3 Interview difficult
- 4 Complete stupor

9. AGITATION

0 None
1 "Playing with" hand, hair, etc.
2 Hand-wringing, nail-biting, biting of lips

10. ANXIETY - PSYCHIC

0 No difficulty
1 Subjective tension and irritability
2 Worrying about minor matters
3 Apprehensive attitude apparent in face or speech
4 Fears expressed without questioning

11. ANXIETY - SOMATIC

0	Absent	Physiological concomitants of anxiety such as:
1	Mild	Gastrointestinal - dry mouth, wind, indigestion,
2	Moderate	diarrhea, cramps, belching
3	Severe	Cardiovascular – palpitations, headaches
4	Incapacitating	Respiratory - hyperventilation, sighing Urinary frequency Sweating

12. SOMATIC SYMPTOMS - GASTROINTESTINAL

0 None
1 Loss of appetite but eating without staff encouragement.
Heavy feelings in abdomen.
2 Difficulty eating without staff urging. Requests or requires
laxatives or medications for bowels or medication for G.I.
symptoms.

13. SOMATIC SYMPTOMS - GENERAL

0 None
1 Heaviness in limbs, back or head, backaches, headache, muscle

aches, loss of energy and fatigability
2 Any clear-cut symptom rates 2

14. GENITAL SYMPTOMS

0	Absent	0	Not ascertained
1	Mild	Symptoms such as: loss of libido,	
2	Severe	menstrual disturbances	

15. HYPOCHONDRIASIS

0	Not present
1	Self-absorption (bodily)
2	Preoccupation with health
3	Frequent complaints, requests for help, etc.
4	Hypochondriacal delusions

16. LOSS OF WEIGHT

A. When Rating by History:

0	No weight loss
1	Probable weight loss associated with present illness
2	Definite (according to patient) weight loss

B. On Weekly Ratings by Ward Psychiatrist, When Actual Changes are Measured:

0	Less than 1 lb. weight loss in week
1	Greater than 1 lb. weight loss in week
2	Greater than 2 lb. weight loss in week

17. INSIGHT

0	Acknowledges being depressed and ill
1	Acknowledges illness but attributes cause to bad food, climate, overwork, virus, need for rest, etc.
2	Denies being ill at all

Total Score: _____

Citation: Hamilton M: A rating scale for depression. Journal of Neurology, Neurosurgery and Psychiatry 23:56-62, 1960

17.3. Social Support Scale

Emotional/informational support	None of the time	A little of the time	Some of the time	Most of the time	All of the time
1. Someone you can count on to listen to you when you need to talk	 1	 2	 3	 4	 5
2. Someone to give you information to help you understand a situation	 1	 2	 3	 4	 5
3. Someone to give you good advice about a crisis	 1	 2	 3	 4	 5
4. Someone to confide in or talk to about yourself or your problems	 1	 2	 3	 4	 5
Tangible support	None of the time	A little of the time	Some of the time	Most of the time	All of the time
9. Someone to help you if you were confined to bed	 1	 2	 3	 4	 5
10. Someone to take you to the doctor if you needed it	 1	 2	 3	 4	 5
11. Someone to prepare your meals if you were unable to do it yourself	 1	 2	 3	 4	 5
12. Someone to help with daily chores if you were sick	 1	 2	 3	 4	 5
Affectionate support	None of the time	A little of the time	Some of the time	Most of the time	All of the time
13. Someone who shows you love and affection	 1	 2	 3	 4	 5
14. Someone to love and make you feel wanted	 1	 2	 3	 4	 5
15. Someone who hugs you	 1	 2	 3	 4	 5
Positive social interaction	None of the time	A little of the time	Some of the time	Most of the time	All of the time
16. Someone to have a good time with	 1	 2	 3	 4	 5
17. Someone to get together with for relaxation	 1	 2	 3	 4	 5
18. Someone to do something enjoyable with	 1	 2	 3	 4	 5

17.4 STRAIN

STRAIN Description

Overview

The Stress and Adversity Inventory (STRAIN) is a secure, online stress assessment system that measures individuals' lifetime exposure to different types of acute and chronic stress that can affect mental and physical health. The system is intended to combine the reliability and sophistication of an interview-based measure of stress with the simplicity of a self-report instrument. To accomplish this goal, the STRAIN enquires about 75 different types of stressors (Adolescent STRAIN) or 55 different types of stressors (Adult STRAIN) that cover all major life domains (e.g., health, intimate relationships, friendships, children, education, work, finances, housing, living conditions, crime, etc.) and several social-psychological characteristics (e.g., interpersonal loss, physical danger, role change, entrapment, etc). Users are presented with one question at a time, which are written in colloquial English, and questions can also be read aloud to users. In turn, users register their responses by simply touching their answer, if an iPad is being used, or by clicking their answer using the computer mouse, if a computer monitor is being used. For each stressor that is endorsed, users are asked a series of short follow-up questions that ascertain the severity, frequency, timing, and duration of the stressor. Using sophisticated interviewing logic, the STRAIN system can guide users through what would amount to a 157-page interview in as little as 20 minutes. Based on the information collected, the system produces 445 raw variables that can be combined to create 115 different stress exposure summary scores and life charts. Analyses can in turn be based on a number of basic factors, including stress severity and exposure timing (e.g., Childhood vs. Distant vs. Recent Life Stress). Because each stressor in the STRAIN is tagged with several attributes, more sophisticated analyses can also be performed by focusing on stressors occurring in specific life domains or that involve particular social-psychological characteristics.

Security Information

The STRAIN was developed in accordance with the best practices in online web security. The online interviewing platform that the STRAIN utilizes is written in PHP and based on a very fast, efficient, and state-of-the-art back-end database software package (LimeSurvey). That package resides on a website that has a dedicated IP address and is hosted on a secure, Comodo SSL-certified internet server that is protected by a comprehensive firewall and continuously monitored by the global leader in website security, SiteLock, for the possibility of a malicious attack. Participant data, which is entirely anonymous, is transferred from users' computers to the server in a secure data channel that utilizes private cookies in conjunction with advanced SSL technology. Finally, all data are stored anonymously on a database that utilizes encrypted password-protected entry to prevent possible participant identification.

Risk Information

Participants will answer questions anonymously through an online survey. No identifying or protected health information will be collected. An Excel file linking participants' identifying information and their STRAIN responses will be kept in an offline location, which will be separate from all STRAIN and other study data. Consequently, participants will not be identifiable or linked to their responses. Prior research using the STRAIN has demonstrated that the interview does not induce negative mood, and that usability and acceptability of the interview is very high. Nevertheless, it is possible that some individuals may feel mildly uncomfortable answering personal questions about their life. Before beginning the interview, individuals are reminded that they are not required to answer questions that they do not feel comfortable answering. Moreover, they may terminate the interview at any time.

Data Analyses

In this study, participants' responses to the STRAIN will be used to calculate a standard set of 20 lifetime stress exposure scores, which are based on the type of stressors experienced, when they were experienced, their primary life domain, and their core social-psychological characteristics. More specifically, this summary score data will include the following computed variables: Lifetime stressor count, lifetime stressor severity, early life stress (before age 18) stressor count, early life stress (before age 18) stressor severity, adulthood stressor count, adulthood stressor severity, lifetime count of acute life events, lifetime count of chronic difficulties, lifetime severity of acute life events, lifetime count of chronic difficulties, lifetime stressor count and severity by primary life domain (i.e., housing, education, work, treatment/health, marital/partner, reproduction, financial, legal/crime, other relationships, death, life-threatening situations, possessions), and lifetime stressor count and severity by core social-psychological characteristic (i.e., interpersonal loss, physical danger, humiliation, entrapment, role change/disruption). In addition, we will compute indices relating each participant's actual overall stress burden, as compared to what would be expected given his or her sex and age (based on prior STRAIN validation data), and their actual overall health status (i.e., number of mental and physical health problems), again, as compared to what would be expected given his or her sex and age (based on prior STRAIN validation data).

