8.2. Analysis of Endpoints

- 1) *Effect of Group Support Psychotherapy:* We will compare the proportion of baseline depression with the proportion of persistent depression at week 26. We will use the PHQ-9 as a continuous variable, with changes from baseline to week 26.
- 2) *Effect of biomarkers on persistent vs. resolved depression:* We will compare those with persistent depression (PHQ-9 ≥ 5 at week 26) versus resolved depression (PHQ-9 < 4 at week 26). We will assess baseline demographic and HIV parameters as well as log₂-transformed plasma cytokines from week 0, week 26, and the change in biomarker values from week 0 to week 26. We will use Benjamini-Hochberg adjustment for multiple comparisons for the biomarkers unrelated to our *a priori* hypothesis (i.e. IL-6 association with persisting depression). If the distribution between groups is unbalanced for an important factor (e.g. age, sex as biological variable, anti-depressant use, HIV viral load), we will adjust as needed for differentially distributed variables between the cohorts. We will consider sex as a biological variable in our analyses, considering differential effects in women vs. men.
- 3) *Effect of biomarkers on depressed vs non-depressed control group:* We will compare those never depressed (PHQ-9 < 5) and those depressed at baseline and at 26 weeks. We will also group those never depressed with those with resolved depression (PHQ-9 < 5 at week 26) and compare with those with persistent depression (PHQ-9 > 4 at week 26). We will assess baseline demographic and HIV parameters as well as log₂-transformed plasma cytokines from week 0, week 26, and the change in biomarker values from week 0 to week 26. We will use Benjamini-Hochberg adjustment for multiple comparisons for the biomarkers unrelated to our *a priori* hypothesis (i.e. IL-6 association with persisting depression). If the distribution between groups is unbalanced for an important factor (e.g. age, sex as biological variable, anti-depressant use, HIV viral load), we will adjust as needed for differentially distributed variables between the cohorts. We will consider sex as a biological variable in our analyses, considering differential effects in women vs. men.

*Depression Defined as PHQ-9 score 5-19 (severely depressed excluded)

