- 5) *Baseline Cytokine Analysis:* As a secondary outcome, subjects will be categorized into baseline groups of mild depression versus moderate or above depression. We will compare baseline plasma biomarker levels by group via linear regression of \log_2 transformed data. Any demographic covariates associated with depression will be included in the regression model. We will also compare by 9 am cortisol levels. We will assess whether age or sex are associated with biomarker responses.
- 6) *Virologic Outcomes:* As a secondary outcome, proportions of those with 26-week virologic suppression will be correlated by those with persisting depression vs. resolved using Fisher's Exact test.
- 7) *Depression Scale Comparison:* We will compare prevalence of depression using the PHQ-9 and the HDRS. We will compare the proportions of those depressed at baseline and 26 weeks using McNemar's test.
- 8) *Social Factors and Stress Assessment:* We will analyze social factors and the STRAIN stress and adversity tool scores by baseline depression groups as well as those with persistent depression at 26 weeks using linear regression.

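### Section 17.4 announces 20 STRAIN scores but lists 44, and the plan names neither a main score nor a multiplicity rule for analysing them

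*Combined protocol and SAP*

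**What the plan says.** Section 17.4, under Data Analyses, states that responses will be used to calculate "a standard set of 20 lifetime stress exposure scores". It then sets out what this summary data will contain:

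- Totals for lifetime, early life and adulthood, each as a count and a severity. The list opens with "Lifetime stressor count, lifetime stressor severity, early life stress (before age 18) stressor count".
- Acute and chronic scores: "lifetime count of acute life events, lifetime count of chronic difficulties, lifetime severity of acute life events, lifetime count of chronic difficulties". The chronic count is printed twice and no chronic severity score appears.
- "lifetime stressor count and severity by primary life domain", followed by 12 named domains.
- Count and severity by five characteristics: "interpersonal loss, physical danger, humiliation, entrapment, role change/disruption".

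A further sentence adds two indices that compare a participant with what is expected for age and sex. It begins "In addition, we will compute indices relating each participant's actual overall stress burden", and the second index concerns overall health status.

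The analysis is in 8.2 item 8: "We will analyze social factors and the STRAIN stress and adversity tool scores by baseline depression groups". The item continues with persistent depression at 26 weeks and gives linear regression as the method. Synopsis item 7 is the same except that it also includes the control group. Neither names a main score, a significance level or an adjustment. Items 2 and 3 of 8.2 do address multiplicity, but only for biomarkers: "We will use Benjamini-Hochberg adjustment for multiple comparisons for the biomarkers", with the prespecified IL-6 hypothesis left outside the adjustment.

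**The concern.** There are two linked gaps. First, the number of scores announced does not match the list that follows it, so the size of the family is undefined. Second, the analysis item refers to scores in the plural, applies them to two contrasts, and does not rank or adjust them. The plan recognises multiplicity for biomarkers but does not extend the same control to a STRAIN family of dozens of variables.

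The risk is selective reporting. An analyst could look across many domain and characteristic scores and present those below 0.05 as correlates of depression or of its persistence. A reader could not tell whether a reported score was the intended one or the best of many. Item 8 also carries no status label. Items 5 and 6 of 8.2 are called secondary outcomes, whereas item 8 is called neither secondary nor exploratory.

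**Working it through.** **Step 1: can the stated 20 be reproduced?** The inputs are all from 17.4, Data Analyses.

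- Named scores: 6 (lifetime, early life and adulthood, count and severity each) + 4 (acute and chronic) = 10 printed. One is a repeat, so 9 are distinct.
- Life domains: 12 × 2 = 24.
- Characteristics: 5 × 2 = 10.
- As printed: 10 + 24 + 10 = **44**. Distinct: 9 + 24 + 10 = **43**. As printed with the two indices: 44 + 2 = **46**.

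Other readings of the list were tried:

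- One score per domain and characteristic: 10 + 12 + 5 = 27.
- Characteristics omitted: 10 + 24 = 34.
- Named scores only: 10.
- Domains omitted: 10 + 10 = 20.

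Only the last gives 20, and it drops the 12 domains that the same sentence includes.

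**Step 2: expected false positives.** Three assumptions are made. Each score is tested separately. The level is two-sided 0.05, which the plan states only for the sample size in 8.1. No score is truly associated with depression. The expected number is then m × 0.05, whatever the correlation between scores:

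- 20 × 0.05 = 1.0
- 44 × 0.05 = 2.2 per contrast
- 88 × 0.05 = 4.4 over two contrasts

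If some associations are real, fewer true nulls remain, so these figures are upper bounds.

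**Step 3: chance of at least one false positive.** For independent tests this is 1 − 0.95^m. For correlated tests, normal test statistics with one common correlation were simulated (100,000 draws). The documents give no correlation between scores, so the values below are assumed.

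| Common correlation | 20 tests | 44 tests (one contrast) | 88 tests (two contrasts) |
|---|---|---|---|
| 0 (independent) | 64.2% | 89.5% | 98.9% |
| 0.3 | 54.0% | 77.3% | 92.5% |
| 0.5 | 41.8% | 59.4% | 75.0% |
| 0.7 | 28.8% | 38.7% | 48.1% |

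Under independence, the count chosen hardly matters: 43 tests give 89.0% and 46 give 90.6%.

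**Step 4: allowing for how the scores are built.** The totals contain their sub-scores, and each count is paired with a severity, so independence is implausible. An illustrative simulation built 44 scores from 55 stressors, the number of stressor types 17.4 gives for the adult STRAIN. It compared 100 with 200 participants in 1,500 runs per setting, and took the tenth named score to be a chronic severity. The chance of at least one false positive in one contrast was 74%, 67% and 48% as the shared tendency to report stressors was increased.

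**The case against.** The strongest objection is that the plan never says every score will be tested. Section 17.4 lists variables to be computed, not hypotheses. Item 8 says only that scores will be analysed. The enrollment and week 26 case report forms each have a single STRAIN score field, which would fit an analysis of one total. This stands: a reader might infer that 44 separate tests per contrast are planned, and the documents do not establish that. What remains is that they leave open one score, 20 or 44, with nothing to fix the choice before results are seen.

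A reader might also infer that a false positive is almost guaranteed. That does not hold. The 98.9% figure needs 88 independent tests, and the scores overlap by construction. In addition, the 2.2 and 4.4 assume no true association at all, whereas the Introduction treats social factors as part of depression in HIV.

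The consequence is limited. STRAIN is absent from the objectives and endpoints in 2.1 and from the sample size in 8.1. No conclusion on PHQ-9, IL-6 or cortisol depends on it.

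Finally, nothing in the documents singles out lifetime count and severity as the main scores, so that choice belongs to the investigators. If both were left unadjusted in both contrasts, four tests would remain, with 1 − 0.95^4 = 18.5% if independent. This is fair, and it is a reason to name one main score if the investigators can.

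**Conclusion.** The point holds as a low-cost improvement. The mismatch between 20 and 44 (43 distinct, 46 as printed with the indices) can be checked from the text and is not a matter of judgement. The absence of a main STRAIN score and of any multiplicity rule for STRAIN is equally plain, and it contrasts with the plan's treatment of biomarkers.

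The size is conditional. With all 44 scores tested at 0.05 and all nulls true, up to 2.2 false positives are expected per contrast. The chance of at least one is 90% if independent and about 39-77% at assumed correlations of 0.7-0.3. Chance findings are likely in that case, but near-certainty is not supported. Nor do the documents support reading this as a threat to the trial's main results. What is at stake is how far any reported link between stress and depression can be trusted.

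**What to change.** In 8.2 item 8, and in synopsis item 7 to match:

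- Name the main STRAIN score or scores in advance, for example lifetime stressor count and lifetime stressor severity.
- Apply the plan's own Benjamini-Hochberg adjustment to the remaining STRAIN scores within each contrast, and report them as exploratory.

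In 17.4, reconcile the stated 20 with the list actually analysed, and resolve the repeated chronic difficulties entry.

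The cost is wording only: no new data, visits or participants. The downside is that fewer domain scores will reach significance.
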